4.3 Baseline data

No formal statistical testing will be performed comparing characteristics at baseline. The following will be presented and summarised by treatment group and overall:

- Cardiac history (covariate used for stratifying at randomisation)
 - (i) conservative non-invasive strategy (invasive coronary angiography is not planned)
 - (ii) invasive coronary angiography is planned but has not yet occurred*
 - (iii) an invasive coronary angiogram has been performed and the patient has been referred or undergone CABG surgery
 - (iv) an invasive coronary angiogram has been performed and the patient has had at least one drug eluting stent implanted
 - (v) an invasive coronary angiogram has been performed and the patient has had only bare metal stents implanted
 - (vi) an invasive coronary angiogram has been performed and the patient is to receive medical management only

*Where possible, it will be summarised which group the participants belong to following their angiogram based on definitions in appendix A.

- Gender and age at randomisation
- Time from date of MI to randomisation
- Derived from data linkage from the participant's electronic health records (appendix B).
 - Index of multiple deprivation
 - Ethnicity
 - Smoking history

¹ The protocol refers to "If there is no substantial heterogeneity in outcome between these two groups, then they can be included in the analysis and further increase the power". Due to recruitment being halted early and the small numbers in these groups, this will be explored in subgroup analyses only and all participants will be included in the ITT analysis population.

- Hypertension
- Diabetes Mellitus
- Hyperlipidaemia
- Ischaemic heart disease
- Myocardial infarction
- Percutaneous coronary intervention
- Coronary artery bypass grafting
- Heart failure
- Ischaemic stroke
- Haemorrhagic stroke
- Chronic kidney disease
- Medications
 - Aspirin
 - Clopidogrel
 - Prasugrel
 - Ticagrelor
 - Lipid lowering therapy
 - Beta-blocker
 - Angiotensin converting enzyme inhibitor or angiotensin receptor blockers
 - Oral anticoagulants

A further descriptive summary will explore any association between the COVID-19 pandemic and UK participant characteristics. The baseline characteristics summary will be stratified by date of lockdown for UK participants: randomisations occurring up to and including 23 March 2020 and those occurring after 23 March 2020.

4.4 Adherence to allocated treatment duration

Adherence data will be summarised, where available.

The average duration of antiplatelet therapy will be summarised descriptively overall and by treatment group.

Adherence will be defined as follows:

- Allocated to 3 months:
A record of prescription of 90% or greater for the first 3 months and 10% or less for months 4-12.
- Allocated to 12 months
A record of prescription of 90% or greater for the first 12 months and 10% or less for months 13-15.

Adherence will be reported descriptively overall and by treatment group.

Note the first month's prescription will be made in hospital and there will be no record of it on routinely collected prescribing data. Therefore participants will be assumed to be adherent for the first month following their date of MI.

4.5.1 Secondary analyses

The comparison between the groups is considering differing lengths of the same treatment; this inherently causes the potential violation of the proportional hazards' assumption. Therefore, in a secondary analysis of the primary outcome all-cause mortality at 15 months from date of MI will be compared between groups using a logistic regression model stratifying by country and adjusting for cardiac history. Results will be presented as an adjusted odds ratio with corresponding 95% CI and p-value.

² Note that we will not censor at date of withdrawal, as we will not have outcome data collected up to the point of withdrawal and therefore withdrawn participants will be excluded from the analysis.

³ The protocol refers to stratifying by centre but due recruitment being halted early and the potential for small number of outcome events per centre, the analysis will only adjust for country and the effect of centre will be explored in a sensitivity analysis.

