5.5 RANDOMISATION

5.5.1 Randomisation Procedures

A web-based computer-generated randomisation process will be used to ensure allocation concealment and reduce bias. The randomisation system will be provided by ECTU and patients will be randomised using their unique health identifier to prevent inadvertent duplicate randomisation. International sites will use their own randomisation system which will be described in their country specific protocol. Randomisation will be by permuted-block with a level of stratification for

each of the following groups of patients: (i) conservative non-invasive strategy (invasive coronary angiography is not planned), (ii) invasive coronary angiography is planned but has not yet occurred, (iii) an invasive coronary angiogram has been performed and the patient has been referred or undergone CABG surgery, (iv) an invasive coronary angiogram has been performed and the patient has had at least one drug eluting stent implanted, (v) an invasive coronary angiogram has been performed and the patient has had only bare metal stents implanted (this group will also include patients who have had balloon angioplasty only performed without stent implantation), (vi) an invasive coronary angiogram has been performed and the patient is to receive medical management only.

Block size will be randomly determined, and each block will contain both treatments in a 1:1 ratio.

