5.5.3 Methods to Ensure Blinding

This is an open-label trial and there will be no masking of treatment allocation or need for unblinding.

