5.6 WITHDRAWAL OF STUDY PARTICIPANTS

Participants are free to withdraw from the study at any point or a participant may be withdrawn by the attending clinician. If a participant wishes to withdraw they will need to contact their local research team who will document the nature and primary reason for withdrawal, if possible. The contact details for the local site will be provided on a study card. Unless the participant specifically withdraws consent any data collected up to the point of withdrawal will be retained and analysed and data will continue to be collected remotely from the participant's medical notes and via data linkage.

Participants who withdraw or are withdrawn from the study will not be replaced.

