9.3 PROPOSED ANALYSES

For the primary outcome (all-cause mortality) we will compare time-to-event in a Cox regression model, stratifying by country and centre to account for clustering of

participants, and adjusting for cardiac history (stratification factor in randomisation). For secondary outcomes of non-cardiovascular mortality and bleeding death, we will similarly estimate cause-specific hazard ratios, censoring for competing causes of death. All analyses will be by intention-to-treat.

It is highly likely that baseline characteristics will have a major influence on the overall clinical benefits and risks [Steg et al, 2011]. We will explore efficacy and safety outcomes in the 4 pre-specified and stratified cohorts nested within the trial: (i) medically managed, (ii) percutaneous coronary intervention with bare metal stent, (iii) percutaneous coronary intervention with drug-eluting stent, and (iv) coronary artery bypass graft surgery.

In a sensitivity analysis, we will consider a two-stage individual participant data (IPD) meta-analysis where the IPD from each country are analysed separately then combined by an appropriate fixed-effect or random effects meta-analysis model [Burke et al, 2017].

The statistical methods will be documented in full in a detailed statistical analysis plan. The methods used will take into account the early stopping of the trial, and the limited numbers of events that will be available for analysis. A composite outcome of non-fatal bleeding and all-cause mortality will be explored.

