4.1 ITT analysis population

The ITT analysis population will include patients who have been randomised into the Dual ACS trial in the UK and New Zealand (NZ) and for whom outcome data are available. Those who subsequently became ineligible after a diagnosis other than Type 1 myocardial infarction (MI) and withdrawn from the trial will be excluded¹.

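### The SAP removes withdrawn and re-diagnosed patients from a set it calls ITT, although the protocol keeps them under linkage unless they withdraw consent

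*SAP*

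**What the plan says.** **Protocol.** Section 5.6 recognises two routes out of the trial: the participant may choose to leave, or "a participant may be withdrawn by the attending clinician". It then sets the data rule: "Unless the participant specifically withdraws consent any data collected up to the point of withdrawal will be retained and analysed and data will continue". The rest of that sentence names medical notes and linkage as the continuing sources. Section 9.3 adds, without qualification, "All analyses will be by intention-to-treat".

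**SAP.** Section 3 adopts intention-to-treat as far as possible. Section 4.1 limits the ITT population to randomised UK and New Zealand patients with outcome data, and adds: "Those who subsequently became ineligible after a diagnosis other than Type 1 myocardial infarction (MI) and withdrawn from the trial will be excluded". Footnote 2, marked in 4.5 and printed under 4.5.1, explains why follow-up is not censored at withdrawal: "we will not have outcome data collected up to the point of withdrawal and therefore withdrawn participants will be excluded from the analysis".

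Footnote 1 is attached to the 4.1 exclusion sentence but deals with another matter, the bypass-surgery and bare-metal-stent groups. It ends: "this will be explored in subgroup analyses only and all participants will be included in the ITT analysis population".

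**The concern.** For a patient who is withdrawn but has not revoked consent, the documents give opposite instructions: the protocol analyses the patient and the SAP does not. Re-diagnosis is not withdrawal of consent, so the 4.1 clause removes patients whom 5.6 keeps.

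These are exclusions after randomisation, from the primary mortality comparison, under an ITT label. Protocol 5.5.3 states: "This is an open-label trial and there will be no masking of treatment allocation". Whoever decides to withdraw a patient, including after a re-diagnosis, can therefore know the allocation. Re-diagnosis is foreseeable, since one randomisation stratum consists of patients for whom "invasive coronary angiography is planned but has not yet occurred". If the patients removed differ between arms in number or prognosis, the mortality comparison is biased.

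**Working it through.** **1. The texts compared**

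| Patient | Protocol 5.6 | SAP |
|---|---|---|
| Withdraws consent | Outside the retention rule | Excluded (footnote 2) |
| Leaves without withdrawing consent | Retained, analysed, linked | Excluded as footnote 2 is worded |
| Withdrawn by clinician | Retained, analysed, linked | Excluded as footnote 2 is worded |
| Re-diagnosed and withdrawn, consent intact | Retained, analysed, linked | Excluded (4.1) |

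The documents clearly agree only on the first row.

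**2. Is the departure flagged or remedied?** Footnotes 1, 3 and 4 each name the protocol provision they change. Footnote 2 does not. The three sensitivity analyses in SAP 4.5.2 (two-stage meta-analysis, 3-month landmark, centre) restore none of these patients. SAP 4.2 tabulates withdrawals by reason and arm, which would show an imbalance but not correct it.

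**3. The plan's own figures.** Protocol 9.2 uses 16.9% mortality in the 12-month arm and a risk ratio of 0.9, hence 15.21% in the 3-month arm. The two-proportion formula (pooled variance, two-sided 0.05, 85% power, no continuity correction) gives 8,472 per group, as stated, and 16,944/0.925 = 18,318.

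**4. Precision available.** Unrounded, p12 = 0.254 × 0.667 = 0.1694 and p3 = 0.9 × 0.1694 = 0.1525; the mean is 0.1609. For the 4,576 UK patients:

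- deaths ≈ 4,576 × 0.1609 = 736
- SE(log HR) ≈ 2/√736 = 0.0737

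This uses a one-year planning rate and leaves out New Zealand.

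**5. Bias from unequal exclusion.** The documents give no exclusion rates, so those below are assumptions. Suppose there is no true effect, a fraction w of an arm is excluded, and mortality in those excluded is m times the average. The remaining risk is proportional to (1 − w·m)/(1 − w), and the apparent RR (3 versus 12 months) is the ratio of that term between arms. For w3 = 1%, w12 = 2%, m = 2: (0.98/0.99)/(0.96/0.98) = 0.9899/0.9796 = 1.0105.

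| w3 | w12 | m | Apparent RR | Shift in SEs | Type I error |
|---|---|---|---|---|---|
| 1% | 2% | 2 | 1.0105 | 0.14 | 5.23% |
| 1% | 3% | 2 | 1.0215 | 0.29 | 5.96% |
| 2% | 1% | 2 | 0.9896 | −0.14 | 5.23% |
| 3% | 1% | 2 | 0.9790 | −0.29 | 5.96% |
| 1% | 2% | 0.5 | 0.9949 | −0.07 | 5.06% |
| 1% | 3% | 0.5 | 0.9897 | −0.14 | 5.22% |
| 2% | 2% | 2 | 1.0000 | 0 | 5.00% |
| 5% | 2% | 2 | 0.9671 | −0.45 | 7.4% |
| 5% | 2% | 3 | 0.9328 | −0.94 | 15.7% |

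The shift is log(RR)/0.0737. Type I error is the chance that a normal variable with that mean and unit variance falls beyond ±1.96. With 4,576/2 = 2,288 UK patients per arm, 1% is about 23 patients and 2% about 46.

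Starting from w3 = 1%, an apparent RR of 1.05 needs 4.4 percentage points of extra exclusion in the 12-month arm at m = 2, or 2.2 at m = 3. If mortality were 5.4% (the trial average in protocol Table 2), deaths would be 4,576 × 0.054 = 247 and the SE 0.127; an RR of 1.0215 would then be a shift of 0.17 SE.

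**6. Power.** With 4,576 patients at the planning rates, power is 34.4% with everyone kept and 33.9% or 33.0% with 2% or 5% excluded. Power is not the issue; bias is.

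**The case against.** The strongest reply is that footnote 2 concerns consent withdrawal only. Its stated reason, that outcome data will not exist, fits that case best, because under 5.6 linkage stops only there. The re-diagnosis clause in 4.1 would also be redundant if footnote 2 already removed everyone withdrawn. On this reading footnote 2 agrees with the protocol and lacks only a clarifying phrase. That is plausible, but the text does not say it, and it leaves the 4.1 exclusion in conflict with 5.6.

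Second, nothing is hidden. Both exclusions are stated in advance, footnote 2 gives a reason, section 3 promises ITT only as far as possible, and 4.1 requires outcome data. This is fair: what is missing is any acknowledgement that 5.6 says otherwise. Those qualifiers do not justify dropping patients whose outcomes the protocol provides for by linkage.

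Third, SAP section 3 allows imputation if enough outcomes are missing, and 4.2 promises the CONSORT numbers. The imputation is conditional, has no threshold and is not aimed at patients excluded as ineligible. The reporting is useful but corrects nothing.

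Fourth, the effect may be small. Protocol 9.2 expects almost no loss to follow-up, only one of six strata awaits a planned angiogram, both arms receive the same treatment for three months, and nothing in the documents shows that re-diagnosis depends on arm. This stands, and limits how serious the point is. The loss-to-follow-up expectation does not, however, address exclusions made by rule.

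**Conclusion.** The concern holds, and the SAP should be changed. The conflict over who enters the primary analysis is certain for re-diagnosed patients who have not withdrawn consent. For other withdrawn patients it follows from footnote 2 as worded.

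The effect on the result is unknown in size and direction. Under the assumed 1 to 2 percentage points of extra exclusion at twice average mortality, the risk ratio moves by about 1% to 2%, against a planned effect of 0.90. Larger distortions need larger or more selective imbalances, and equal exclusion of similar patients causes none. These figures rest on planning mortality, UK numbers and invented exclusion rates and mortality multiples. They show what is possible, not what is expected.

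**What to change.** - Define *withdrawn* in the SAP, separating withdrawal of consent to use of linked data from every other kind.
- Define the ITT set as all randomised UK and New Zealand patients, analysed as allocated and followed by linkage, removing only those who withdrew that consent.
- Keep re-diagnosed patients who have not withdrawn consent in the primary analysis; exclude them in one added sensitivity analysis.
- Extend the 4.2 table to show exclusions from the analysis set by arm and reason.
- If linked data for some withdrawn patients cannot be obtained, say why, name the departure from protocol 5.6 as footnotes 1, 3 and 4 do for theirs, and call the set modified ITT.

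The cost is SAP wording, one extra analysis, and linkage that protocol 5.6 already provides for. The documents do not show whether that linkage can still be obtained, hence the last item.

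Keeping re-diagnosed patients dilutes the effect slightly. If 2% do not have type 1 infarction, have the same baseline risk and get no effect, a risk ratio of 0.90 becomes 0.98 × 0.90 + 0.02 × 1 = 0.902.

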4.5.2 Sensitivity analyses

Two-stage individual participant data (IPD) meta-analysis

In a sensitivity analysis, we will consider a two-stage individual participant data (IPD) meta-analysis[2]. The first stage will analyse the IPD from each country separately as per the analysis model described above in section 4.5. In the second stage, we will combine the individual estimates using a fixed effect inverse-weighted meta-analysis model of adjusted log hazard ratios. The results will be presented as adjusted HRs with 95% confidence intervals for each study and the pooled estimate. A random effects (DerSimonian and Laird method) model will also be estimated to check the robustness of the findings (irrespective of the degree of heterogeneity).

Landmark analysis

Both randomised groups receive the same treatment for the first 3 months and therefore would expect, apart from random chance, to observe no difference in outcomes. In a second sensitivity analysis, we will therefore perform a landmark analysis including only those participants who have survived at 3 months from date of MI. The analysis will be performed as per the analysis model described above in section 4.5

Adjusting for centre

In a third sensitivity analysis, the analysis model specified in section 4.5 will also include stratifying by centre to determine the robustness of the results. In the event of issues with model fitting, this will be performed for Scottish participants only which comprise most randomised participants.

4.5.3 Subgroup analysis

A priori sub-groups for the primary outcome will be explored as follows:

- i. medically managed (including conservative non-invasive strategy)
- ii. percutaneous coronary intervention with bare metal stent
- iii. percutaneous coronary intervention with drug-eluting stent
- iv. coronary artery bypass graft surgery.

If the number of events is sufficient, these analyses will be performed by including an interaction term between treatment group and the covariate in the Cox proportional hazards regression model described in Section 4.5 above. Otherwise, no formal analyses will be undertaken and summaries only of primary outcome events will be presented for each of the subgroups, split by treatment group.

In the event of problems due to small numbers in the subgroups, the groups will be combined as follows: any stent (combining bare metal and drug-eluting stents); and any intervention (combining bare metal and drug-eluting stents and coronary artery bypass graft surgery).

The subgroup analysis will be performed with and without those with a cardiac history of 'invasive coronary angiography is planned but has not yet occurred'. They will be included in the group to which they belong following their angiogram based on definitions in appendix A.

4.5.4 Assessing the impact of COVID-19

The impact of COVID-19 is expected to be minimal due to the study design. Study-related procedures encompass a single 30-minute contact with the patient who is already in a hospital ward or attending an out-patient facility. All follow up is through routinely collected health record data and the drugs are prescribed as part of standard of care. The primary outcome of all-cause mortality is objective and should not be influenced by lockdown restrictions.

An exploratory analysis will summarise descriptively the primary outcome by treatment group and stratified by the date of the lockdown for UK participants: randomisations occurring up to and including 23 March 2020 versus those occurring after 23 March 2020.

4.6 Secondary outcomes

The interpretation of trial findings for secondary outcomes will focus on the effect size and 95% CI. No formal adjustment will be made to significance levels to allow for multiplicity.

For each of the following secondary outcomes (appendix C), events are defined as the time to first outcome event during follow-up from date of the index myocardial infarction. Follow-up will be censored at competing causes of death or 15 months from date of MI, whichever occurs first.

Efficacy

- Cardiovascular death and non-fatal myocardial infarction
- Cardiovascular mortality (cardiac and non-cardiac)
- Myocardial infarction (fatal and non-fatal)
- Stent thrombosis
- Coronary revascularisation
- Thrombotic stroke

Safety

- Non-cardiovascular death (including fatal bleeding) and major non-fatal bleeding
- Non-cardiovascular death (including fatal bleeding)
- Major fatal and non-fatal bleeding
- Hospitalisation for bleeding
- Intracranial haemorrhage
- Gastrointestinal bleeding

The analysis will follow that specified for the primary outcome in section 4.5. The number and proportions of participants with an event for individual components of the secondary outcomes will also be reported alongside the composite.

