4.6.1 Sensitivity analyses

Competing risk of death

To take into account the possibility of a competing risk of death, a Fine and Gray[3] proportional sub-distribution hazards regression model will be used to take into account the competing risk of death to provide reassurance about the robustness of the analysis. The effect of the randomised intervention will be presented by the sub-distribution hazard ratio and 95% confidence interval. The cumulative incidence function (CIF) obtained from the Fine-Gray model will be plotted separately for each intervention; the median time to event and its 95% CI will be reported by intervention group. The absolute risk difference (and its 95% CI) will also be reported at the median time to event.

Diagnostic position

The analysis of secondary safety outcomes, will consider the occurrence of an event if the diagnostic codes, as defined in Appendix C, occur in any diagnostic position.

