4.8 Additional outcomes

We will explore the composite outcome of non-fatal bleeding and all-cause mortality. This will be analysed using the same approach as for the primary outcome in section 4.5. The number and proportions of participants with an event for the individual components of the outcome will be reported alongside the composite.

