Appendix C

Outcomes defined used the following codes and positions specified below following the date of index MI unless otherwise specified. If the code is not identified in any admissions/deaths then they will be assumed to not have the outcome of interest.

Data sources

Scotland: SMR00 / SMR01 / NRS Deaths / Prescribing Information System / Scottish Blood Transfusion Database

England: Hospital Episode Statistics / Civil Registrations of Death / Medicines dispensed in Primary Care (NHSBSA data)

Outcome	Code (ICD-10 , OPCS4)
All-cause mortality	Any record of death.
Non-cardiovascular death (including fatal bleeding) and major non-fatal bleeding	
Death due to a non-cardiovascular cause
 
Primary position for cause of death
 
Ax, Bx, Cx, Dx Ex, Fx , Gx , Hx , Jx, Kx , Lx , Mx , Nx , Ox , Px , Qx , Rx , Sx , Tx , Ux , Vx , Xx , Yx , Zx.
 
OR
 
Hospitalisation for bleeding
 
Primary or first secondary position
 
I60x, I61x, I62x, S06.4x, S06.5x, S06.6x, K92.0x, K92.1x, K 92.2x, I85.0x, I98.3x, K22.6x, K25.0x, K25.2x, K25.4x, K25.6x, K26.0x, K26.2x, K26.4x, K26.6x, K27.0x, K27.2x, K27.4x, K27.6x, K28.0x, K28.2x, K28.4x, K28.6x, K29.0x, K62.5x, K66.1x, R58x, I23.0x, I31.2x, I69.0x, I69.1x, I69.2x, H21x, H35.6x, H31.3x, H43.1x, H44.8x, H45.0x, R04.0x, R04.1x, R04.2x, R04.8x, R04.9x, T81.0x, D62x, N83.7x, N93.8x , N93.9x, O03.1x, O03.6x, O04.1x, O04.6x, O05.1x, O05.6x, O06.1x, O06.6x, O20.8x, O20.9x, O46x , O67x, O07.1x, O07.6x, O08.1x, O71.7x , O72.0x , O72.1x , O72.2x , O90.2x , P26.1x , R31x , M25.0x.
 
OR

	
Primary procedure position (OPSC4)
 
E05x , E058x , E059x , F162x , D041x , E203x , F365x , G523x , H212x , H531x , K681x , P093x , P271x , T301x , Y221x , T032x , Y221x , T032x , Y321x , V032x , A052x , A053x , A054x , A103x , A401x , A411x

Non-cardiovascular death (including fatal bleeding)	
Primary cause of death
 
Ax , Bx , Cx , Dx , Ex , Fx , Gx , Hx , Jx , Kx , Lx , Mx , Nx , Ox , Px , Qx , Rx , Sx , Tx , Ux , Vx , Xx , Yx , Zx

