Hospitalisation for bleeding	
Hospitalisation for bleeding
 
Primary or first secondary position
 
I60x, I61x, I62x, S06.4x, S06.5x, S06.6x, K92.0x, K92.1x, K 92.2x, I85.0x, I98.3x, K22.6x, K25.0x, K25.2x, K25.4x, K25.6x, K26.0x, K26.2x, K26.4x, K26.6x, K27.0x, K27.2x, K27.4x, K27.6x, K28.0x, K28.2x, K28.4x, K28.6x, K29.0x, K62.5x, K66.1x, R58x, I23.0x, I31.2x, I69.0x, I69.1x, I69.2x, H21x, H35.6x, H31.3x, H43.1x, H44.8x, H45.0x, R04.0x, R04.1x, R04.2x, R04.8x, R04.9x, T81.0x, D62x, N83.7x, N93.8x , N93.9x, O03.1x, O03.6x, O04.1x, O04.6x, O05.1x, O05.6x, O06.1x, O06.6x, O20.8x, O20.9x, O46x , O67x, O07.1x, O07.6x, O08.1x, O71.7x , O72.0x , O72.1x , O72.2x , O90.2x , P26.1x , R31x , M25.0x.
 
OR
 
Primary procedure position (OPCS4)
 
E05x , E058x , E059x , F162x , D041x , E203x , F365x , G523x , H212x , H531x , K681x , P093x , P271x , T301x , Y221x , T032x , Y221x , T032x , Y321x , V032x , A052x , A053x , A054x , A103x , A401x , A411x

Intracranial haemorrhage	
Intracranial haemorrhage event
 
Primary or first secondary position
 
I60x , I61x , I62x , S06.5x , S06.6x.

	
OR
 
Death due to intracranial haemorrhage
 
Primary cause of death
 
I60x , I61x , I62x , S06.5x , S06.6x.

Gastrointestinal bleeding	
Gastrointestinal bleeding event
 
Primary or first secondary position
 
K92.0x , K92.1x , K 92.2x , I85.0x , I98.3x , K22.6x , K25.0x , K25.2x , K25.4x , K25.6x , K26.0x , K26.2x , K26.4x , K26.6x , K27.0x , K27.2x , K27.4x , K27.6x , K28.0x , K28.2x , K28.4x , K28.6x , K29.0x , K62.5x , K55.2x , K66.1x.
 
OR
 
Death due to Gastrointestinal bleeding
 
Primary cause of death
 
K92.0x , K92.1x , K 92.2x , I85.0x , I98.3x , K22.6x , K25.0x , K25.2x , K25.4x , K25.6x , K26.0x , K26.2x , K26.4x , K26.6x , K27.0x , K27.2x , K27.4x , K27.6x , K28.0x , K28.2x , K28.4x , K28.6x , K29.0x , K62.5x , K55.2x , K66.1x.

Cardiovascular mortality and non-fatal myocardial infarction	
Death due to a cardiovascular cause
 
Primary cause of death
 
Ix
 
OR
 
Myocardial infarction after the Index Admission Discharge Date

	
Primary or first secondary position
 
I21x, I22x

Cardiovascular mortality (cardiac and non-cardiac)	
Death due to a cardiovascular cause
 
Primary cause of death
 
Ix

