Myocardial infarction (fatal and non- fatal)	
Myocardial infarction after the Index Admission Discharge Date
 
Primary or first secondary position
 
I21x, I22x
 
OR
 
Death due to myocardial infarction
 
Primary cause of death
 
I21x, I22x

Stent thrombosis	
Stent thrombosis
 
Primary or first secondary position
 
T82.8x

Coronary revascularisation	
Coronary revascularisation after the Index Admission Discharge Date
 
Primary procedure position (OPCS4)

	K40x, K41x, K42x, K43x, K44x, K45x, K46x, K47x, K48x, K49x, K50x, K75x.
Thrombotic stroke	
Ischaemic stroke
 
Primary or first secondary position
 
I63x
 
OR
 
Death due to ischaemic stroke
 
Primary cause of death
 
I63x

Blood transfusion	Any record of transfusion
Iron therapy	
Prescribed Iron Therapy
 
Approved drug names: FERROUS SULPHATE, FERROUS FUMARATE, FERROUS GLUCONATE, FERRIC MALTOL, FERROUS CALCIUM CITRATE, FERROUS GLYCINE SULFATE, IRON CARBOXYMALTOSE, SODIUM FEREDETATE, IRON CARBOXYMALTOSE, IRON DEXTRAN, IRON SUCROSE, VENOFER, FERINJECT

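### Non-fatal secondary outcomes are counted from the index MI, not from randomisation, so events that precede allocation are included and dilute the ratios

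*SAP*

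**What the plan says.** Protocol 4.2 admits patients whose type 1 MI was diagnosed up to 12 weeks earlier. Protocol 5.1 recruits from hospital wards; SAP 4.5.4 also mentions out-patient attendance, so randomisation after discharge is possible.

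For secondary outcomes, SAP 4.6 says "events are defined as the time to first outcome event during follow-up from date of the index myocardial infarction", with censoring at a competing death or at 15 months from the MI. Appendix C sets the search window: "Outcomes defined used the following codes and positions specified below following the date of index MI unless otherwise specified". The exceptions are non-fatal MI ("Myocardial infarction after the Index Admission Discharge Date") and revascularisation ("Coronary revascularisation after the Index Admission Discharge Date"). Both move the start to index discharge, not to randomisation.

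The same window reaches further:
- The composite of non-fatal bleeding and death in SAP 4.8: "This will be analysed using the same approach as for the primary outcome in section 4.5".
- The descriptive outcomes in SAP 4.7; transfusion, for example, is defined in Appendix C as "Any record of transfusion".
- The SAP 4.6.1 sensitivity analysis of safety outcomes, which "will consider the occurrence of an event if the diagnostic codes, as defined in Appendix C, occur in any diagnostic position".
- The SAP 4.5.1 analysis, in which 15-month status "will be compared between groups using a logistic regression model", if it is carried over to secondary outcomes by the cross-reference in 4.6.

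**The concern.** Allocation cannot influence an event that happened before it. Such events have an expected ratio of 1 between the arms, so including them moves hazard and odds ratios towards 1 when the true effect is not null. In a time-to-first-event analysis, an early event also hides a later one that did occur on trial.

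The exposure is realistic. In four of the six randomisation strata (protocol 5.5.1, iii to vi) angiography precedes randomisation, and protocol 1.2 links arterial access to bleeding. The bleeding definitions in Appendix C carry no index-discharge rule, so a procedural bleed before randomisation counts if it is coded in an eligible position. The any-position analysis admits more of these. MI and revascularisation are exposed only in patients randomised after discharge.

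No planned analysis removes these events. The 3-month landmark in SAP 4.5.2 is written for the primary outcome and conditions on survival only. The 4.6.1 analyses deal with competing risk and diagnostic position.

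SAP 4.6 bases interpretation of secondary outcomes on effect size and confidence interval, and bleeding is the harm that the shorter duration is meant to reduce. Dilution could understate that benefit.

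**Working it through.** The plan gives no figure for this effect, and no distribution of the delay, so the size has to be shown as a range.

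**Inputs**
- Hazard ratio for bleeding 0.58 (protocol 9.2, illustrative), applied in months 3-12 only. The ratio is 1 in months 0-3 (both arms on the same therapy, SAP 4.5.2) and in months 12-15 (assumed).
- Flat bleeding hazard (protocol 11.6 calls the risk continuous).
- Assumed 15-month bleeding risk of 4% in the 12-month arm.
- 4,576 / 2 = 2,288 patients per arm.
- Delay from MI to randomisation spread uniformly over 1, 4 or 12 weeks, or a mixture (assumed).

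**Approximation for rare events**

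Counted from the MI, HR ≈ 1 − 9 × (1 − 0.58) / 15 = 1 − 3.78 / 15 = 0.748.

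Counted from randomisation with mean delay m months, HR ≈ 1 − 3.78 / (15 − m). This holds because every delay ends before month 3 (84 days against about 91). With 30.44 days per month:
- Over 1 week, m = 3.5 / 30.44 = 0.115: 1 − 3.78 / 14.885 = 0.746.
- Over 4 weeks, m = 14 / 30.44 = 0.460: 1 − 3.78 / 14.540 = 0.740.
- Over 12 weeks, m = 42 / 30.44 = 1.380: 1 − 3.78 / 13.620 = 0.722.

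First bleeds before randomisation, both arms: the monthly hazard is −ln(0.96) / 15 = 0.00272, so the count is about 4,576 × 0.00272 × m, or 1.4, 5.7 and 17.

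**Numerical solution of the large-sample Cox equation** (total counted from the MI: 160.3 events, 91.5 and 68.8 by arm; SE of log HR = √(1/91.5 + 1/68.8) = 0.160)

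| Delay | HR from MI | HR after fix | Events before randomisation | Log-HR shift / SE |
|---|---|---|---|---|
| 1 week | 0.748 | 0.746 | 1.4 | 0.02 |
| 90% 1 week, 10% 12 weeks | 0.748 | 0.744 | 3.0 | 0.03 |
| 75% 1 week, 25% 12 weeks | 0.748 | 0.740 | 5.4 | 0.06 |
| 4 weeks | 0.748 | 0.740 | 5.7 | 0.07 |
| 12 weeks | 0.748 | 0.722 | 17.1 | 0.22 |

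At 12 weeks the odds ratio moves from 0.744 to 0.719, but the risk difference only from 0.993 to 0.996 percentage points.

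**Sensitivity of the 12-week shift (0.026)**
- With 2% or 6% risk it stays at 0.026.
- With a ratio of 0.7 or 0.8 in months 3-12 it falls to 0.018 or 0.012.
- If 30% or 50% of the bleeding hazard fell in months 0-3 (60% of that in month 1), the HR would move from 0.780 to 0.731 or from 0.844 to 0.775. With delays over 1 week the same cases shift by only 0.005 to 0.006.

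**Ischaemic events.** Using the clopidogrel interval rates in protocol Table 1 for shape only, 4%, 17% and 35% of events counted from the MI would precede randomisation for delays over 1, 4 and 12 weeks. The assumed effect is small (ratios 1/0.96, 1/0.94 and 1/0.86 in months 3-6, 6-9 and 9-12; 3% risk), so the HR moves only from 1.029 to 1.031, 1.036 and 1.046.

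**SAP 4.8 composite** (4% bleeding; 16.9% one-year mortality, HR 0.9 in months 3-12). The largest change is 0.9028 to 0.9012, at 12 weeks.

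**The case against.** The best reply is that the effect is too small to change any reading. Twelve weeks is an eligibility ceiling, not a typical delay, and recruitment is mainly on wards. If nearly everyone is randomised within a week, the bleeding ratio moves by 0.002 with a flat hazard. Even in the 12-week case, dropping events raises the standard error from 0.160 to 0.169: z goes from 1.82 to 1.92 and the 95% interval from 0.55-1.02 to 0.52-1.01. The shifts of 0.05 to 0.07 need both long delays and early clustering of bleeding, which sits badly with the protocol's description of a continuous risk. All of this stands, and it is why the point is minor.

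Three further points also stand:
- Dilution towards 1 is true in expectation and only when there is an effect. Chance imbalance in a handful of early events could move the estimate either way.
- Events after randomisation but before month 3 also carry an expected ratio of 1, so the fix removes only part of the dilution.
- The 35% ischaemic share is illustrative. It bears mainly on stroke and stent thrombosis, because MI and revascularisation already start at discharge and deaths cannot precede randomisation. The documents give no time course for stroke or stent thrombosis.

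Delayed entry can also be called unnecessary, since the date restriction alone gives the same hazard ratios to four decimals. It does no harm and keeps the risk sets correct.

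The hardest practical case is an index admission that spans randomisation, because codes attach to admissions. A dating rule is needed there and the plan has none. None of these arguments supplies a reason to count events that allocation could not have caused.

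**Conclusion.** The concern holds and is minor. The SAP's stated window counts non-fatal events that precede randomisation, and no planned analysis removes them. Under the base assumptions the bleeding hazard ratio is diluted by 0.002 to 0.008 for delays up to 4 weeks and by 0.026 if delays run evenly to 12 weeks. It could reach about 0.07 if half the bleeding hazard also fell in the first 3 months. These figures rest on the assumed 4% risk, the illustrative ratio of 0.58 and an unknown delay distribution. Neither arm is favoured, risk differences barely change, and the primary mortality hazard ratio and the death-only outcomes are not affected. SAP 4.3 already tabulates the MI-to-randomisation interval, so the actual size can be established.

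**What to change.** In SAP 4.6, 4.8 and Appendix C:
- Count a non-fatal outcome only if it is dated after randomisation. Keep the index-discharge rule for non-fatal MI and revascularisation, so that these count from the later of randomisation and discharge. Add no discharge rule for bleeding, stroke or stent thrombosis.
- Keep the MI time scale and the 15-month horizon, and enter patients in the Cox models for these outcomes at randomisation. For revascularisation, and for non-fatal MI if analysed without deaths, enter at the later of randomisation and discharge. Outcomes that include deaths keep entry at randomisation, so that in-hospital deaths after randomisation are not lost.
- Apply the date restriction alone to the logistic model and the 4.6.1 analyses when used for secondary outcomes, and to the 4.7 summaries.
- If the 3-month landmark is used for secondary outcomes, count only events after 3 months.
- State which date an event takes when an admission spans randomisation, so that in-hospital bleeds after randomisation are kept. Report the number of excluded events by arm.

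Appendix B and the mortality Cox, Kaplan-Meier and RMST analyses need no change beyond noting that they describe patients who survived to randomisation.

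The cost is SAP wording, one date restriction and an entry time in the models, using dates already planned for collection. Counted bleeds in the base case fall from 160 to 159, 155 or 144 for delays over 1, 4 or 12 weeks; the events lost carry no information on treatment. The dating rule for spanning admissions is the one part that needs real thought.
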